		LIST OF IN-TEXT FIGURES	
	Figure 1.	Study Schema	13

LIST OF ABBREVIATIONS

ADA anti-drug antibody AE adverse event

AEI adverse events of interest
ALT alanine aminotransferase
AML acute myeloid leukemia
AST aspartate aminotransferase

BICR blinded independent central review BLQ below the limit of quantitation

BMI body mass index
CBC complete blood count

CC-486 Onureg

cCR cytogenetic complete remission
CFR Code of Federal Regulations

CI confidence interval CK creatine kinase

COVID-19 Coronavirus disease 2019
CR complete remission

CRh complete remission with partial hematologic recovery
CRi complete remission with incomplete hematologic recovery
CR_{MRD}
complete remission without minimal residual disease

CR_{MRD+/unk} complete remission with positive or unknown minimal residual disease

CRF case report form
CSR clinical study report

CTCAE Common Terminology Criteria for Adverse Events

DILI drug-induced liver injury
DLT dose-limiting toxicity
DMC data monitoring committee

DOR duration of response ECG electrocardiogram

ECOG Eastern Cooperative Oncology Group

EFS event-free survival
EOT end of treatment
FAS Full Analysis Set
Hb hemoglobin
HLT high-level term

ICH International Conference on Harmonization (of Technical Requirements for Registration of

Pharmaceuticals for Human Use)

IV intravenous ITT intent to treat

LTT lower-level term

LOQ limit of quantitation

MDS myelodysplastic syndrome

MedDRA Medical Dictionary for Regulatory Activities

MEC mitoxantrone, etoposide, and cytarabine

MLFS morphologic leukemia-free state

MRD minimal residual disease
MST MedDRA Search Term
ORR overall response rate
OS overall survival
PK pharmacokinetic
PR partial remission

PRO Patient reported outcome

PT preferred term

Q1, Q3 first quartile, third quartile

QRS electrocardiographic deflection between the beginning of the Q wave and termination of the

S wave representing time for ventricular depolarization

QT electrocardiographic interval between the beginning of the Q wave and termination of the

T wave representing the time for both ventricular depolarization and repolarization to occur

QTc QT interval corrected for heart rate

QTcF QT interval corrected for heart rate using Fridericia's formula

RBC red blood cell

RDI relative dose intensity
RO receptor occupancy

RP2D recommended Phase 2 dose

RR electrocardiographic interval representing the time measurement between the R wave of one

heartbeat and the R wave of the preceding heartbeat

SAP statistical analysis plan
SCT stem cell transplantation
SI (units) international system of units
SMQ Standardised MedDRA Queries

SOC system organ class StD standard deviation

TEAE treatment-emergent adverse event

TF treatment failure

TFLs tables, figures, and listings
ULN upper limit of normal
WHO World Health Organization

PHARMACOKINETIC ABBREVIATIONS

AUC_{last} area under the concentration versus time curve from time zero to the last quantifiable

concentration

AUC_{tau} area under the concentration versus time curve over the dosing interval

C_{last} last observed quantifiable concentration of the drug

C_{max} maximum observed concentration of drug

C_{tau} observed drug concentration at the end of the dosing interval CLss/F apparent oral clearance after administration of the drug:

at steady state: $CLss/F = Dose/AUC_{tau}$, where "Dose" is the dose of the drug

t_{1/2} estimate of the terminal elimination half-life of the drug, calculated by dividing the natural log of

2 by the terminal elimination rate constant (λ_z)

 $T_{last} \hspace{1cm} \text{time (observed time point) of } C_{last} \\ T_{max} \hspace{1cm} \text{time (observed time point) of } C_{max} \\$

 λ_Z terminal elimination rate constant, estimated by linear regression of the terminal elimination

phase of the concentration of drug versus time curve

1. INTRODUCTION

This statistical analysis plan (SAP) describes the statistical analysis methods and defines key elements including variable definitions for analysis of data of Study GS-US-546-5920 in support of the clinical study report (CSR). This SAP is based on the study protocol amendment 6 dated 02 November 2023. Any changes made after the finalization of the SAP will be documented in the CSR.

1.1. Study Objectives and Endpoints

Objectives and endpoints are presented by cohort in Sections 1.1.1, 1.1.2, and 1.1.3.

1.1.1. Safety Run-in Cohort 1 and Phase 2 Cohort 1 (1L Unfit AML Mag+Ven+Aza)

Primary, secondary, CCI objectives and endpoints for patients with newly diagnosed, previously untreated acute myeloid leukemia (AML) who are ineligible for intensive chemotherapy are as follows:

[figure not shown]
Primary Objective(s)		Primary Endpoint(s)		
Ef	ficacy			
•	To evaluate the efficacy of magrolimab in combination with the anti-leukemia therapy venetoclax + azacitidine as determined by the complete remission (CR) rate (Phase 2 Cohort 1)	•	CR rate, defined as the proportion of patients who achieve CR as determined by the investigator based on prespecified criteria (Phase 2 Cohort 1)	
Sa	fety			
•	To evaluate the safety and tolerability, and to determine the recommended Phase 2 dose (RP2D) of magrolimab in combination with the anti-leukemia therapy venetoclax + azacitidine (Safety Run-in Cohort 1)	•	Incidence of dose-limiting toxicities (DLTs), treatment- emergent adverse events (AEs), and laboratory abnormalities according to the National Cancer Institute (NCI) Common Terminology Criteria for Adverse Events (CTCAE) Version 5.0 (Safety Run-in Cohort 1)	

Secondary Objective(s) Secondary Endpoint(s) Efficacy/Safety/PK delineate objectives and endpoints as appropriate. Overall response rate (ORR), including CR, complete To evaluate additional measures of efficacy of magrolimab in combination with the anti-leukemia remission with incomplete hematologic recovery (CRi), therapy venetoclax + azacitidine complete remission with partial hematologic recovery (CRh), partial remission (PR), and morphologic To evaluate the safety and tolerability of magrolimab in leukemia-free state (MLFS) combination with the anti-leukemia therapy venetoclax + azacitidine (Phase 2 Cohort 1) CR/CRi rate To evaluate the pharmacokinetics (PK) of magrolimab Complete remission without minimal residual disease in combination with the anti-leukemia therapy (CR_{MRD-}) rate venetoclax + azacitidine Complete remission or complete remission with partial To evaluate the immunogenicity of magrolimab in hematologic recovery (CR/CRh) rate combination with the anti-leukemia therapy venetoclax Cytogenetic complete remission (cCR) + azacitidine Duration of responses (DOR) Duration of CR Duration of CR/CRi Duration of CR/CRh Event-free survival (EFS) Overall survival (OS) Red blood cell (RBC) transfusion independence rate Platelet transfusion independence rate Incidence of treatment-emergent AEs and laboratory abnormalities according to the NCI CTCAE Version 5.0 (Phase 2 Cohort 1) Magrolimab concentrations over time Rate and magnitude of anti-magrolimab antibodies

1.1.2. Safety Run-in Cohort 2 and Phase 2 Cohort 2 (R/R AML Mag+MEC)

Primary, secondary, CCI objectives and endpoints for patients with relapsed or refractory (R/R) AML are as follows:

[figure not shown]
Primary Objective(s)	Primary Endpoint(s)		
Efficacy			
To evaluate the efficacy of magrolimab in combination with the anti-leukemia therapy mitoxantrone, etoposide, and cytarabine (MEC) as determined by the CR rate (Phase 2 Cohort 2)	CR rate, defined as the proportion of patients who achieve CR as determined by the investigator based on prespecified criteria (Phase 2 Cohort 2)		
Safety			
To evaluate the safety and tolerability, and to determine the RP2D of magrolimab in combination with the anti-leukemia therapy MEC (Safety Run-in Cohort 2)	Incidence of DLTs, treatment-emergent AEs, and laboratory abnormalities according to the NCI CTCAE Version 5.0 (Safety Run-in Cohort 2)		
Secondary Objective(s)	Secondary Endpoint(s)		
Efficacy/Safety/PK delineate objectives and endpoints as	appropriate.		
 To evaluate additional measures of efficacy of magrolimab in combination with the anti-leukemia therapy MEC To evaluate the safety and tolerability of magrolimab in combination with the anti-leukemia therapy MEC (Phase 2 Cohort 2) To evaluate the PK of magrolimab in combination with the anti-leukemia therapy MEC To evaluate the immunogenicity of magrolimab in combination with the anti-leukemia therapy MEC 	 ORR, including CR, CRi, CRh, PR, and MLFS CR/CRi rate CR_{MRD} rate CR/CRh rate cCR DOR Duration of CR Duration of CR/CRi Duration of CR/CRh EFS OS RBC transfusion independence rate Platelet transfusion independence rate Incidence of treatment-emergent AEs and laboratory abnormalities according to the NCI CTCAE Version 5.0 (Phase 2 Cohort 2) Magrolimab concentrations over time Rate and magnitude of anti-magrolimab antibodies 		

1.1.3. Safety Run-in Cohort 3 and Phase 2 Cohort 3 (Post-Chemo Maint Mag+CC-486 [Onureg])

Primary, secondary, CCI objectives and endpoints for patients with newly diagnosed AML who are in CR or CRi with MRD positivity following intensive chemotherapy are as follows:

Primary Objective(s)		Primary Endpoint(s)		
Efficacy				
	To evaluate the efficacy of magrolimab in combination with anti-leukemia therapy CC-486 (Onureg) as determined by the MRD negative CR rate (Phase 2 Cohort 3)	•	MRD negative CR rate, defined as the proportion of patients who maintain CR as determined by the investigator based on prespecified criteria and reach MRD negative disease status as determined using multiparameter flow cytometry with a sensitivity of < 0.1% (Phase 2 Cohort 3)	
Sa	fety			
 To evaluate the safety and tolerability, and to determine the RP2D of magrolimab in combination with the anti-leukemia therapy CC-486 (Safety Run-in Cohort 3) 		•	Incidence of DLTs, treatment-emergent AEs, and laboratory abnormalities according to the NCI CTCAE Version 5.0 (Safety Run-in Cohormalities)	

1.2. Study Design

This is a Phase 2, open-label, multicenter, multi-arm study to evaluate magnolimab in combination with anti-leukemia therapies in patients with AML. This trial includes safety run-in cohorts and Phase 2 cohorts.

The study schematic is presented in Figure 1.

Figure 1. Study Schema

Cohort 1: 1L Unfit AML Mag+Ven+Aza: Phase 2 Safety run-in (N=6) Safety Newly diagnosed, evaluation and Magrolimab + venetoclax previously untreated AML Magrolimab + RP2D + azacitidine patients, ineligible for venetoclax + azacitidine intensive induction N = 40chemotherapy Cohort 2: R/R AML Mag+MEC: Safety run-in (N=6) Phase 2 Safety evaluation and AML patients who are Magrolimab + MEC RP2D refractory or relapsed Magrolimab + MEC after intensive induction N = 30chemotherapy Cohort 3: Post-chemo Maint Mag+CC-486: Phase 2 Safety run-in (N=6) Safety evaluation and AML patients in CR or CRi Magrolimab + CC-486 RP2D with intensive induction Magrolimab + CC-486 chemotherapy who are N = 40MRD+

AML = acute myeloid leukemia; MEC = mitoxantrone, etoposide, and cytarabine; MRD = minimal residual disease; RP2D = recommended Phase 2 dose

Up to approximately 164 patients will be enrolled in the study, with up to 54 patients in the safety run-in cohorts and approximately 110 patients in the Phase 2 cohorts.

Initially, 6 patients will be enrolled into Safety Run-in Cohorts 1, 2, and 3, respectively. A DLT assessment period of 1 cycle (28 days) will occur.

Dose de-escalation decisions will be made as follows:

- If no more than 2 patients in a safety run-in cohort experience a DLT in Cycle 1, enrollment into the corresponding Phase 2 cohort will begin at this dose level.
- If 3 or more (> 33%) patients in a safety run-in cohort experience a DLT up to the end of Cycle 1, another 6 patients will be enrolled in that cohort at a lower dose and evaluated in the same manner to define the RP2D.

After completion of each safety run-in cohort and identification of the RP2D for that cohort, the corresponding Phase 2 cohort may be enrolled, with 40 patients in Phase 2 Cohorts 1 and 3 each and 30 patients in Cohort 2.

Study treatment regimens comprise the following:

Safety Run-in Cohort 1 and Phase 2 Cohort 1

- Magrolimab 1 mg/kg intravenous (IV)
- Magrolimab 15 mg/kg IV
- Magrolimab 30 mg/kg IV
- Azacitidine 75 mg/m² subcutaneous or IV
- Venetoclax 100 mg oral tablets
- Venetoclax 200 mg oral tablets
- Venetoclax 400 mg oral tablets

Safety Run-in Cohort 2 and Phase 2 Cohort 2

- Magrolimab 1 mg/kg IV
- Magrolimab 15 mg/kg IV
- Magrolimab 30 mg/kg IV
- Mitoxantrone 8 mg/m² IV
- Etoposide 100 mg/m² IV
- Cytarabine 1000 mg/m² IV

Safety Run-in Cohort 3 and Phase 2 Cohort 3

- Magrolimab 1 mg/kg IV
- Magrolimab 15 mg/kg IV
- Magrolimab 30 mg/kg IV
- CC-486 300 mg oral tablets

Details about study treatments for each safety run-in cohort, dose de-escalation plans for each safety run-in cohort, and schedules of treatment administration are presented in the study protocol section 3.2.

Duration of treatment will be as follows:

- Cohorts 1 and 3: treatment until discontinuation criteria is met.
- Cohort 2: treatment for up to 12 months.

Clinical response will be assessed by the investigator using prespecified criteria (Appendix 2, also protocol Appendix 7).

Response assessments will be done in conjunction with bone marrow assessments, according to the schedule of assessments (protocol Appendix Table 2 and Appendix Table 3). Bone marrow assessments (including aspirate and core/trephine biopsy) are required for response assessments and may be used for blast evaluation, MRD assessment, cytogenetics, RO (to be collected at selected study sites), and correlative studies. Peripheral blood smears for blasts should be done on the day of the bone marrow assessments.

If the patient is cytopenic at the time of the bone marrow assessment, complete blood count (CBC) is to be monitored at least once per week until optimal count recovery is reached. The best accompanying laboratory CBC result within the \pm 2-week window is to be used to support an efficacy response assessment, with the date of response assigned as the date of bone marrow assessment. If a patient achieves a CR, subsequent bone marrow biopsies are still required to be performed in accordance with the schedule of assessments.

Bone marrow aspirate and biopsy slides or blocks for efficacy assessments will be prepared for potential evaluation of response assessments by independent central review.

Response assessment will be obtained at the EOT visit, unless a prior response assessment has been performed within the last 30 days or progressive disease has been documented.

1.3. Sample Size and Power

Sample size calculations for each of the Phase 2 cohorts are as follows:

- For Cohort 1, a sample size of 46 (40 patients in Phase 2 Cohort 1 together with 6 patients in Safety Run-in Cohort 1) provides an 83.6% power for a 1-group Chi-square test at 1-sided alpha of 0.1 level to detect a CR rate of ≥ 53% for the combination compared with a historical control CR rate of 36.7% {DiNardo 2020}.
- For Cohort 2, a sample size of 36 (30 patients in Phase 2 Cohort 2 together with 6 patients in Safety Run-in Cohort 2) provides a 83.1% power for a 1-group Chi-square test at 1-sided alpha of 0.1 level to detect a CR rate of ≥ 35% for the combination compared with a historical control CR rate of 19% {Greenberg 2004}.
- For Cohort 3, a sample size of 46 (40 patients in Phase 2 Cohort 3 together with 6 patients in Safety Run-in Cohort 3) provides a 78.4% power for a 1-group Chi-square test at 1-sided alpha of 0.1 level to detect an MRD negative CR rate of ≥ 33% for the combination compared with a historical control MRD negative CR rate of 20% {Roboz 2020}.

2. TYPE OF PLANNED ANALYSIS

2.1. Interim Analyses

Prior to the final analysis, interim analyses may be conducted, and the analyses may be submitted to regulatory agencies to seek guidance for the overall clinical development program.

2.2. Primary Analysis

The primary analysis will be conducted after all patients have discontinued the study or have been on study for at least 24 weeks and completed the Week 24 response assessments, outstanding data queries have been resolved or adjudicated as unresolvable, and the data have been cleaned and finalized for the analysis.

The primary analysis was conducted using data extracted on October 18, 2023 with the data cutoff date of June 1, 2023.

2.3. Final Analysis

The final analysis will be performed after all patients have discontinued the study, outstanding data queries have been resolved or adjudicated as unresolvable, and the data have been cleaned and finalized.

3. GENERAL CONSIDERATIONS FOR DATA ANALYSES

Analysis results will be presented using descriptive statistics. For categorical variables, the number and percentage of patients in each category will be presented; for continuous variables, the number of patients (n), mean, standard deviation (StD) or standard error (SE), median, first quartile (Q1), third quartile (Q3), minimum, and maximum will be presented.

By-patient listings will be presented for all patients in the All Enrolled Analysis Set, unless otherwise specified, and sorted by patient ID number, visit date, and time (if applicable). Data collected on log forms, such as AEs, will be presented in chronological order within the patient. Age at Day 1 (ie, visit day 1, study day 1, first dosing date of study drug), sex at birth, race, and ethnicity will be included in the listings, as space permits.

3.1. Analysis Sets

Analysis sets define the patients to be included in an analysis. Analysis sets and their definitions are provided in this section. The analysis set will be identified and included as a subtitle of each table, figure, and listing.

For each analysis set, the number and percentage of patients eligible for inclusion will be summarized by cohort.

A listing of reasons for exclusion from analysis sets will be provided by patient.

3.1.1. All Enrolled Analysis Set

The All-Enrolled Analysis Set includes all patients who receive a study patient identification (ID) number in the study after screening. This will be the primary analysis set for analyses of patient demographics and baseline characteristics, enrollment, and disposition.

3.1.2. Full Analysis Set

The Full Analysis Set (FAS) includes all enrolled patients who receive at least 1 dose of any study treatment, with treatment group designated according to the assigned treatment. This is the primary analysis set for efficacy analysis.

3.1.3. Safety Analysis Set

The Safety Analysis Set includes all patients who receive at least 1 dose of study treatment, with treatment assignments designated according to the actual treatment received. This analysis set will be used in the analyses of safety endpoints, as well as study treatment administration.

3.1.4. Dose-Limiting Toxicity (DLT) Evaluable Analysis Set

The DLT Evaluable Analysis Set includes all patients in the Safety Analysis Set who are enrolled in the safety run-in cohorts, have safety assessments through the protocol-specified DLT assessment window (first 4 weeks of study dosing, inclusive), and fulfill the criteria for evaluation for DLT specified in the protocol Section 3.1.1.

During the DLT assessment window, if a patient fails to receive sufficient study treatment for reasons other than DLT, another patient will be enrolled at the same dose level for replacement. For patients who are replaced but received at least 1 dose of any study drug, they will be included in the Safety Analysis Set and not in the DLT Evaluable Analysis Set.

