7.1.7. Additional Analysis of Adverse Events

7.1.7.1. Dose Limiting Toxicity

A DLT is defined as any Grade 4 or higher hematologic toxicity or Grade 3 or higher nonhematologic toxicity (that has worsened in severity from pretreatment baseline) during the 4-week DLT assessment period and is related to magnolimab or magnolimab combination.

For each cohort being evaluated for safety and tolerability based on DLT assessment, DLT evaluable patients are identified as those who either experienced a DLT any time during the DLT Assessment Period or completed at least certain amount of the drug administration during the DLT Assessment Period. A summary of DLT will be presented by Preferred Term and Severity.

A listing of the DLT AEs will be provided by cohort including cohort number, patient ID, actual dose amount prior to or on the start date of the AE, DLT term from investigator as well as CTCAE term and associated severity grade, if available.

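### The SAP gives two incompatible definitions of a DLT-evaluable patient; the one in Section 3.1.4, read literally, drops a run-in patient who has a DLT and then dies or leaves the study before Week 4.

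*SAP*

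**What the plan says.** Section 3.1.4 starts from run-in patients in the Safety Analysis Set and adds that they must "have safety assessments through the protocol-specified DLT assessment window (first 4 weeks of study dosing, inclusive), and fulfill the criteria for evaluation" laid down in protocol Section 3.1.1. The conditions are joined by an 'and', and none is waived for a patient who has had a DLT. The same section provides for replacement: "if a patient fails to receive sufficient study treatment for reasons other than DLT, another patient will be enrolled at the same dose level".

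Section 7.1.7.1 gives a second rule. DLT evaluable patients are "those who either experienced a DLT any time during the DLT Assessment Period or completed at least certain amount of the drug administration". This is an either/or rule, and it does not require follow-up to the end of the window. The section also sets the grade threshold: "A DLT is defined as any Grade 4 or higher hematologic toxicity or Grade 3 or higher nonhematologic toxicity", so a fatal event can be a DLT.

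Section 1.2 gives the setting. The window is one 28-day cycle and each run-in cohort starts with six patients. The de-escalation trigger reads "If 3 or more (> 33%) patients in a safety run-in cohort experience a DLT up to the end of Cycle 1". Sections 1.1.1 and 1.1.2 make DLT incidence a primary endpoint of the run-in cohorts, and Section 5.1 reports the DLT-evaluable count in the disposition table.

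**The concern.** A programmer cannot satisfy both definitions. Under 7.1.7.1 a DLT is enough to be evaluable. Under 3.1.4 the same patient must also have been assessed through Week 4. The two part company for patients whose follow-up ended early, and among patients with a DLT these may include the most serious cases.

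The exclusion is selective. Among DLT patients, 3.1.4 removes those whose follow-up ended early and never those who stayed, so for them its error runs in one direction, towards a lower DLT incidence. With about six evaluable patients per cohort, one patient changes the reported result visibly. At stake are the reported value of a primary run-in endpoint and the size of the set it is based on.

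**Working it through.** The SAP states no DLT rate or count, so there is no figure of its own to reproduce. The check compares the two rules and then sizes the difference.

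**Step 1. Apply both rules to each kind of run-in patient** (protocol criteria assumed met where the patient had enough drug or a DLT).

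| Patient | Section 3.1.4 | Section 7.1.7.1 |
|---|---|---|
| DLT, assessed through Week 4 | in | in |
| DLT, then death, withdrawal or loss before Week 4 | **out** | **in** |
| No DLT, enough drug, assessed through Week 4 | in | in |
| No DLT, enough drug, not assessed through Week 4 | **out** | **in** |
| No DLT, too little drug | out, replaced | out |

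The rules disagree in the second and fourth rows.

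**Step 2. Effect of dropping DLT patients.** Let x of n patients have a DLT and let k of them leave early. Section 7.1.7.1 reports x/n and Section 3.1.4 reports (x − k)/(n − k). Replacement applies only to under-treatment for reasons other than DLT, so the denominator falls too. The difference is

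x/n − (x − k)/(n − k) = k(n − x) / [n(n − k)],

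which is never negative. With n = 6 (Section 1.2) and k = 1:

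- x = 3: 3/6 = 50.0% becomes 2/5 = 40.0%
- x = 2: 2/6 = 33.3% becomes 1/5 = 20.0%
- x = 1: 1/6 = 16.7% becomes 0/5 = 0%

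In each case the DLT-evaluable count falls from 6 to 5.

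**Step 3. Effect on average, over a range of assumptions.** Let p be the true DLT rate and q the share of DLT patients who die or leave before the window ends. Both are assumptions, as the SAP gives neither. If all patients without a DLT are fully followed, the expected incidence in the 3.1.4 set is p(1 − q)/(1 − pq).

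| p (incidence under 7.1.7.1) | q = 0.10 | q = 0.25 | q = 0.50 |
|---|---|---|---|
| 20% | 0.180/0.980 = 18.4% | 0.150/0.950 = 15.8% | 0.100/0.900 = 11.1% |
| 33% | 0.297/0.967 = 30.7% | 0.2475/0.9175 = 27.0% | 0.165/0.835 = 19.8% |
| 50% | 0.450/0.950 = 47.4% | 0.375/0.875 = 42.9% | 0.250/0.750 = 33.3% |

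If q = 0, the two rules agree on DLT patients.

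**Step 4. The other disagreement.** A patient without a DLT who had enough drug but incomplete follow-up stays in the denominator under 7.1.7.1 and leaves it under 3.1.4. With two DLTs among six patients, that is 2/6 = 33.3% against 2/5 = 40.0%. This pushes incidence the opposite way, so the net difference in a given cohort depends on who left and why.

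**The case against.** The strongest reply is that 3.1.4 is loosely drafted and not a different rule. Its replacement sentence covers only under-treatment for reasons other than DLT, which suggests that DLT patients were meant to count. Protocol Section 3.1.1, not available here, may say so. This is a fair reading of intent, but it does not repair the text: 3.1.4 adds the assessment condition to the protocol criteria with an 'and', so nothing in those criteria can bring the patient back. One could also read the condition as assessed for as long as assessment was possible, but the section specifies the first 4 weeks, inclusive, and gives no such exception.

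Other parts of the reply stand and limit the point:

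- A reader might infer that the recommended Phase 2 dose rests on a DLT count biased downward, or that 3/6 becoming 2/5 crosses the de-escalation boundary. The SAP does not support this. The rule in Section 1.2 counts patients in a run-in cohort with a DLT up to the end of Cycle 1 and does not name this analysis set. Section 6.4 states that all run-in patients in Cohorts 1 and 2 received the recommended dose and that Cohort 3 enrolled no one, so no dose decision is pending.
- A reader might suppose that the dropped patient is replaced and the result becomes 2/6. Section 3.1.4 does not provide for replacing a patient under-treated because of a DLT, so calculations on that basis do not apply.
- Stopping drug alone does not trigger the exclusion. The treatment-emergent period in Section 7.1.5.1 runs to 70 days after the last dose, or to the day before new anticancer therapy if that is earlier, so safety follow-up does not end with dosing. Death, withdrawal or loss to follow-up within the window is what matters.
- Such events would not vanish from the report. Section 7.1.7.1 requires a listing of DLT events, and Sections 7.1.6.1 and 7.1.6.2 report fatal events and deaths within 30 days of first dose on the Safety Analysis Set.

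**Conclusion.** The contradiction is in the current text and holds. Sections 3.1.4 and 7.1.7.1 define the same set differently, and 3.1.4 followed literally excludes a run-in patient who has a DLT and then dies, withdraws or is lost before Week 4. One such patient in a cohort of six lowers the reported DLT incidence by 10 to 17 percentage points when one to three DLTs occurred (16.7% to 0%, 33.3% to 20%, 50% to 40%), and lowers the DLT-evaluable count by one.

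The consequence is confined to reporting a primary run-in endpoint and the disposition table; no effect on dose selection is shown. The size depends on whether any run-in patient had a DLT and left early, which the SAP does not reveal. If none did, and no patient without a DLT had enough drug but incomplete follow-up, the two definitions give the same set.

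**What to change.** Use one definition in both sections. The set should include every run-in patient who had a DLT in the window, regardless of later follow-up, plus every run-in patient without a DLT who has safety assessments through the window and meets the evaluability criteria in the protocol. This adds a DLT branch to 3.1.4 and the full-window condition for patients without a DLT to 7.1.7.1, and so settles both disagreements.

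Then recheck the reported run-in DLT counts and the DLT-evaluable line of the disposition table against the reconciled set. The listing of reasons for exclusion from analysis sets, already planned in Section 3.1, identifies any patient affected. The cost is one reworded sentence, a matching reference in 7.1.7.1 and a check of about six evaluable patients in each of the two enrolled cohorts. No new data are needed.
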